8.3 Contrast agents dosing and administration

Clinical Standard of Care MRI:

Gadolinium is the preferred contrast agent, when subject qualifies (per institutional policy, see section 8.4.2) for gadolinium infusion, but is not required. In subjects that are already enrolled and have underwent at least one gadolinium enhanced MRI, but do not qualify to get Gadolinium at subsequent imaging time points, non-contrast enhanced MRI can be used as clinical MRI.

Dosing of Gadoteridol: After acquiring precontrast images, gadoteridol (Prohance®, Bracco Pharm) will be injected using a power injector. An IV bolus of 0.1 mmol/kg at a flow rate of

up to 3 mL/s will be administered, followed by a saline flush during the first DSC sequence. The appropriate volume of gadoteridol is based on the subject's weight (0.2 ml/kg gadoteridol = 0.1 mmol/Kg) followed by a 20ml saline flush.

Ferumoxytol Imaging

Ferumoxytol imaging consists of two consecutive days of imaging (early and delayed) and will be performed only at time points described in the Schedule of Events (Section 6).

1. Early intravascular phase scan ferumoxytol imaging

Dosing of ferumoxytol: The total dose of ferumoxytol (AMAG Pharmaceuticals, Inc., Cambridge MA) will be 7mg/kg (not exceeding 510mg total). The ferumoxytol will be mixed with normal saline 1:1 solution to dilute to 15mg/ml. 1 mg/Kg IV will be injected at the start of the 7th dynamic cycle during the DSC acquisition at a flow rate of 3ml/s followed by 20ml saline flush. The rest of the ferumoxytol will be given as IV injections at a low flow rate (.1ml/s) followed by 20mg saline flush. The flow rates may be adjusted at the physician's discretion.

2. Delayed (24h) parenchymal phase ferumoxytol scan (optional)

No contrast agent will be given during this MRI.

8.4 Image processing

Image processing will be done at OHSU.

8.4.1 For CNS lesions:

SS-CBV maps will be created using the high resolution T2*w scans before and after contrast agent and $\Delta R2^*$ maps will be created using the formula $\Delta R2^* = \ln(SI_{pre}/SI_{post})/TE$, in which SI_{pre} and SI_{post} indicate the signal intensities pre- and post ferumoxytol, and TE is the echo time. DSC-CBV maps from gadoteridol DSC will be created using a mathematical leakage correction method in NordicICE (Nordic Neurolab, Bergen, Norway) an FDA approved perfusion MRI software (if gadoteridol could not be given per institutional protocol in section 8.4.2, only ferumoxytol maps will be used). The coregistration and overlay of CBV maps on T1-w MPRAGE will be done using NordicICE as well [36, 42]. The clinical MR sequences, such as T1 weighted scans with and without gadoteridol, and T2 weighted pre contrast scans will also be read. Images will be read by 2 radiologists. The radiologists will be blinded to the type of CBV maps (SS and DSC) and subject information.

8.4.2 Oregon Health & Science University policy on assessment of lab results prior to gadolinium based contrast media

For patients with the following risk factors, a serum creatinine level will be obtained with calculation of eGFR according to the following guidelines:

- 1) Creatinine/eGFR NOT required:
 - Dialysis patients – No eGFR required
 - Dialysis patients are excluded from the requirements in numbers 2 and 3 below.

- 2) Creatinine/eGFR required within 24 hours of MRI scan:
 - All inpatients (includes Daypatients and ER patients)
 - Outpatients whose most recent eGFR<60

- 3) Creatinine/eGFR required within 30 days of MRI scan:
 - Patients >60 years of age
 - Outpatients with a history of hypertension requiring medication
 - Outpatients with diabetes mellitus
 - Outpatients with kidney disease: kidney transplant, single kidney, kidney cancer, kidney surgery
 - Outpatient children < 1 year of age

The technologist or RN will notify the radiologist for the following:

- 1) Patient has a history of NSF (Nephrogenic Systemic Fibrosis)
- 2) Patient is on dialysis
- 3) Patients with eGFR <30 mL/min/1.73m²
- 4) Patient received gadolinium based contrast media within the past 24 hours
- 5) For questions related to kidney function or patient history

Informed Consent: The radiologist will obtain informed consent and document risk/benefit of procedure in the patient's medical record for any of the following patients who will be receiving IV gadolinium-based contrast:

- 1) Patients with eGFR<30
- 2)) Patients on dialysis

8.4.3 For systemic lesions

With immunotherapy treatment, an increase in total tumor burden of previously stable systemic lesions (tumor flare reaction) has been described [1]. Based on the location of the systemic lesions, and the feasibility of MR imaging, subjects will be offered optional MR imaging of systemic lesions, to evaluate response as part of the exploratory endpoints. Only subjects with measureable, but stable, systemic involvement at the time of enrollment, will be considered for this imaging. Subjects must provide additional consent for this optional portion of the study.

Fractional Blood Volume (fBV), Vessel Size Index (VSI), and Vessel Density Index (VDI) values will be obtained by defining a region of interest over the entire tumor area. This process will be repeated for 3 central slices of the tumor for every lesion, and the mean value within the region of interest (ROI) will be calculated. T2 and T2* values will be obtained, using GRE and SE data respectively, by plotting mean ROI value at each echo, and calculating the best-fit exponential decay function. R2 and R2* will be defined as the inverse of T2 or T2* values; DR_2 , DR_2^* will be calculated as the ratio of values before and after iron contrast injection.

Fractional Blood Volume of the tumor was derived from the relationship of DR_2^* , fractional blood volume (fBV) and magnetic field constants (ρ, B_0) to changes in magnetic susceptibility, D_c .

$$\begin{aligned} D_c &= \frac{3}{4\rho} \frac{DR_{2,muscle}^*}{fBV_{muscle}\rho B_0} \\ &= \frac{3}{4\rho} \frac{DR_{2,tumor}^*}{fBV_{tumor}\rho B_0} \\ \frac{3}{4\rho} \frac{DR_{2,muscle}^*}{fBV_{muscle}\rho B_0} &= \frac{3}{4\rho} \frac{DR_{2,tumor}^*}{fBV_{tumor}\rho B_0} \\ fBV_{tumor} &= fBV_{muscle} \frac{DR_{2,tumor}^*}{DR_{2,muscle}^*} \end{aligned}$$

where fBV_{muscle} is assumed to be a constant of 3%.

Vessel Size Index will be computed using the following equation:

$$VSI = 0.424 \left(\frac{ADC}{\rho D_c B_0} \right)^{1/2} \frac{DR_2^*}{DR_2}$$

For normalized value calculations, the first two terms will be considered to be constant for all images and will be therefore disregarded.

Vessel Density Index was computed as follows:

$$VDI = 329 \frac{DR_2}{DR_2^*}$$

As for the VSI calculations, the first term in the VDI equation will be disregarded during calculation of normalized values.

Paramagnetic maps will also generated by calculating VSI,VDI and fBV values on a voxel-by-voxel basis. Histograms will be obtained by plotting vessel indices within a tumor region-of-interest against the frequency of occurrence.

Data will be reported as fBV, VSI and VDI +/- standard error of the mean.

8.5 Tumor Tissue Collection and Correlative Blood Biomarker Studies

8.5.1 Blood Biomarkers (optional)

- Correlate clinical and radiological response with systemic immune responses using multicolor flow cytometry, measuring total T-cells (CD3+) with CD4/CD8 ratio,
- T-Reg (CD4+/CD127-/bright CD25+), DNT (CD3+/CD4-/CD8-), Naïve T (CD3+/CD45RA+), memory T (CD3+/CD45RO+), T-cell activation (CD3+/variable CD69+/variable CD25+/variable HLA-DR), NK and NK-activation (CD3-/CD56+/variable CD16+), total B-cells (CD19+), naïve B-cells (CD19+/IgD-/CD27-), memory B-cells (CD19+/IgD-/CD27+).
- Blood will be collected just prior to first dose of pembrolizumab, at 12 weeks after radiosurgery, at suspicion of radiographic progression, and 6 weeks after suspected radiographic progression.
- Blood samples will be collected at OHSU and processed at the OHSU research laboratory.

8.5.2 Tissue Biomarkers

PD-L1 testing will be performed by the CRO QualTek Molecular Laboratories. Any archived tissue samples or tissue obtained from brain biopsy prior to enrollment (archival tissue) and those obtained at suspected radiographic progression will be sent to the CRO for PD-L1 expression assay. We will correlate outcomes and imaging findings with PD-L1 expression in archival systemic tumor tissue, brain biopsy prior to enrollment, and tissue obtained at persistent radiographic progression. Frozen tissue and fixed tissue blocks from initial lung biopsies will be used. In a subset frozen sections and fixed tissue blocks from subjects who undergo resection of brain metastases for clinical indications will also be utilized.

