2.1 Trial Diagram

3.0 OBJECTIVES & RATIONALE

Primary Objective

1. Determine the sensitivity and specificity of relative cerebral blood volume (rCBV) measured by steady state MRI with ferumoxytol in predicting true vs pseudoprogression after SRS and intravenous (IV) pembrolizumab in subjects with brain metastases from NSCLC.

Rationale: This study is not powered to test any formal hypothesis and we aim to collect preliminary data on the sensitivity and specificity of rCBV measurements with ferumoxytol in the primary objective.

Secondary Objectives

1. Evaluate the safety and tolerability of pembrolizumab when given with SRS in subjects with brain metastasis.
2. Evaluate progression free survival, overall survival, best response in brain disease, best response in systemic disease, and duration of best responses of brain and systematic diseases.

Rationale: Given the small sample size, we aim to collect preliminary data on survival, safety, tolerability and efficacy of pembrolizumab when given with SRS in subjects with brain metastasis. No additional toxicity profile is expected when pembrolizumab is used in combination with SRS and ferumoxytol. Toxicities will be evaluated using CTCAE version

4.0. Subjects will have ongoing toxicity evaluation, with documentation of infusion related reactions (grade 3, 4), hematologic toxicities (grade 3, 4) and all other grade 3, 4 toxicities. Each toxicity will be attributed to pembrolizumab and ferumoxytol or neither/both.

Exploratory Objectives

1. Compare the immune response as determined by the volume, pattern and intensity of delayed (24hr) ferumoxytol uptake between subjects who develop true vs pseudoprogression.
2. Investigate the serum immunological parameters and correlate clinical as well as radiological response with systemic immune response to pembrolizumab as measured by immunological panel.
3. Compare the changes percentage expression in PDL-1 in the biopsy tissue before and after therapy at the time of progression.
4. In subjects with measurable systemic lesions, investigate the feasibility of measuring vascular volume fraction (VVF), vessel size index (VSI) and vessel density index (VDI) as surrogate for response (true vs. pseudoprogression, as measured with RECIST 1.1 criteria).

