4.8.4 Biomarker Research End Points

Blood Biomarker

The number and type of T cell can suggest response to immunotherapy in various cancers [68]. This exploratory study will look at serum immune cell subtypes at various time points and correlate them with radiographic and clinical outcomes. This is further elaborated in section 8.5.

Tissue Biomarker

The type and number of tumor infiltrating immune cells including lymphocytes and macrophages correlate with prognosis [69]. Data in melanoma and breast cancer suggest a correlation between the immunophenotype to treatment response [70, 71]. This study will explore the changes in the PDL-1 expression (before and after therapy with pembrolizumab) and types of tumor infiltrating immune cells with radiographic and clinical outcomes. This is further elaborated on in section 8.5.

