8.2 Response assessment

8.2.1 Brain Lesions:

Complete response (CR): Complete disappearance of all enhancing abnormalities on clinical enhanced MRI scan (in the absence of gadolinium, ferumoxytol enhancement will be used). Some subjects will have a small but persistent enhancing abnormality on MRI related to biopsy or focal hemorrhage. It is often difficult to ascertain whether this represents a residual nidus of tumor or scar tissue. Adjunctive radiologic studies such as SPECT or PET as clinically indicated may be helpful, but often the nature of these abnormalities may only be determined by following the subject with serial scans. If this type of abnormality does not change or slowly involutes over time off therapy and corticosteroids, it is reasonable to categorize it as a CR.

Partial Response (PR): At least 50% decrease in the contrast enhancing lesion seen on MRI as compared to baseline imaging. In the event of multiple lesions, the determination of partial response will be based on the sum of the bi-dimensional measurements (greatest diameter x greatest perpendicular) across lesions AND no new sites of disease

Stable disease (SD): less than a PR but is not progressive disease.

Progressive disease (PD):

- **Suspected Radiographic Progression:** progression will be defined by a 20% increase in volume of enhancement compared to the best response on clinical standard of care MRI. At any time point if progression is suspected on the clinical scan, additional steady state ferumoxytol MRI will be performed within 7 days of the clinical scan. Progression will then be confirmed with a follow up scan in 4 weeks +/-5 days with a clinical standard of care MRI scan and additional ferumoxytol scan.
- **Persistent Radiographic Progression:** sustained and evident progression greater than increase in volume of enhancement compared to best response on a follow up scan at least 4 weeks after the scan where progression was suspected as per RANO BM form arm 1 or RANO criteria for subjects in arm 2. In cases with persistent radiographic progression the date of initial scan when progression was suspected will be considered to be the date of progression.
- Appearance of any new lesion or site of disease in the brain during or at the end of therapy.

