- **Confirmation of true progression:** For the purpose of this study, Histopathologic evidence of viable tumor cells in patients with persistent radiographic progression will be define to have confirmed true progression. True progression is confirmed by histopathology, Pembrolizumab will be stopped and patient will be taken off-study.. Patients who refuse biopsy or biopsy is not deemed clinically necessary will be taken off study at persistent radiographic progression. However, they will be continued to be monitored with clinical MRI scan and until death.
- **Pseudoprogression (PsP):** for the purpose of this pilot study, PsP may be confirmed by imaging or by pathology.
 - PsP Imaging: stable or decrease in volume of enhancement at 4 weeks (± 5 days) after suspected radiographic progression.
 - PsP pathology: No viable tumor tissue is seen by histopathology evaluation on tissue obtained after confirmed radiographic progression by imaging.
- **Clinical progression:** Subjects may be removed from study if they experience symptomatic deterioration without radiographic evidence of disease progression.

Not evaluable (NE): Only relevant if any of the target lesions had additional interventions for clinical managements, patient is unable to get follow up scans or images are of poor quality.

Duration of Best Response: The duration of best response is measured from the time measurement criteria are met for SD, CR or PR (whichever is first recorded) until the first date that recurrent or PD is objectively documented (taking as reference for PD the smallest measurements recorded since the treatment started).

Progression free survival and overall survival will be calculated from the date of diagnosis to the date of confirmed progression or death, respectively. The date of diagnosis was used because the time between the date of diagnosis and the start of treatment or date of enrollment may vary due to subject variables or logistical issues based on radiation planning.

8.2.2 Systemic Lesions:

Measurements based on RECIST version 1.1 will be used to make a diagnosis of suspected systemic progression; it will be confirmed using irRC at follow-up.

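### PD-L1 in tissue taken at persistent progression is correlated with outcomes as if it were a baseline marker, although the progression date precedes the tissue, survival from diagnosis includes guaranteed time, and histology is read from the same specimen

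*Combined protocol and SAP*

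**What the plan says.** Section 8.5.2 lists three tissues in one sentence, for a planned correlation of "outcomes and imaging findings with PD-L1 expression in archival systemic tumor tissue, brain biopsy prior to enrollment, and tissue obtained at persistent radiographic progression". The first two are pre-treatment samples and the third is not. Outcomes are not defined there. Section 4.8.4 adds an intention to relate PD-L1 change and "types of tumor infiltrating immune cells with radiographic and clinical outcomes".

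The trial's outcomes are in Section 3.0: "Evaluate progression free survival, overall survival, best response in brain disease, best response in systemic disease, and duration of best responses". Section 8.2.1 fixes their dates. For persistent progression, "the date of initial scan when progression was suspected will be considered to be the date of progression". For the time origin, "Progression free survival and overall survival will be calculated from the date of diagnosis to the date of confirmed progression or death, respectively".

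Surgery is considered only after persistent progression is confirmed (Sections 7.2 and 7.4.3.1). The pathologist then calls progression if viable carcinoma is present and pseudoprogression if it is not (Section 7.2). Section 8.2.1 says the same: "PsP pathology: No viable tumor tissue is seen by histopathology evaluation on tissue obtained after confirmed radiographic progression by imaging".

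The SAP (Sections 10.0 and 10.2) offers two-sample tests or correlation measures as appropriate. It gives no landmark, no time origin at the tissue date and no rule for specimens without tumour.

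**The concern.** A marker measured after treatment can inform only what comes after it or what is measured alongside it. Three features of the plan cut across this for the progression tissue.

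- **Order.** The first progression event is dated before the tissue exists, and best response up to that progression will usually be settled too. PD-L1 in this tissue cannot predict either.
- **Guaranteed time.** Nobody contributes this tissue without surviving to surgery. If PD-L1 moves with time on pembrolizumab, it will correlate with the time before surgery and hence with OS from diagnosis, even if it says nothing about survival afterwards. Exploratory Objective 3 looks for change in PD-L1 over therapy, so drift is a possibility the trial itself takes seriously.
- **Shared specimen.** In operated subjects the true/pseudoprogression label and the PD-L1 value come from the same tissue. If PD-L1 is scored on tumour cells, a tumour-free specimen has nothing to score.

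The pilot could then report progression-tissue PD-L1 as a marker of survival or of true progression when the association comes from the time origin or the label. Section 10.2 says these analyses look for preliminary signals, and Section 4.8.3.1 says the pilot's data will be used to power a larger study.

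**Working it through.** The plan gives no figure for this correlation, so there is none to reproduce.

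**1. Timeline.** Section 8.2.1 places the confirming scan 4 weeks after suspicion; Section 7.4.3.1 places it at 6 weeks. These passages need to be reconciled, but under either one the progression date precedes the tissue by at least 4 to 6 weeks, before visit windows. If suspicion first arises at the scheduled scan 12 weeks after radiation, tissue comes no earlier than 12 + 4 = 16 or 12 + 6 = 18 weeks after radiation. A subject with this tissue has survived that long.

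**2. OS from diagnosis.**

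- From the plan (Section 10.1): 15 subjects operated.
- Assumed: time to surgery T1 and survival after surgery T2 are independent exponentials with equal means. PD-L1 is linked to T1 by a Gaussian copula with correlation 0.3, 0.5 or 0.7 and is unrelated to T2.
- Test: Spearman, two-sided 5%.
- OS is taken as T1 + T2, or as G + T1 + T2, where G is an independent exponential gap from diagnosis to treatment with the same mean. Section 8.2.1 says this gap varies.

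False-positive rates across repeated simulation runs:

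| Setting | 0.3 | 0.5 | 0.7 |
|---|---|---|---|
| n = 15, no gap | about 10% | 21–22% | 38–42% |
| n = 15, with gap | 8–9% | about 16% | 25–27% |
| n = 10, no gap | about 8% | 15–16% | 25–26% |
| n = 10, with gap | 7–8% | 11–12% | 18–19% |
| Survival counted from surgery | about 5% | about 5% | about 5% |

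With zero correlation between PD-L1 and T1, the rate against OS from diagnosis is also about 5%.

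A second simulation checked the size of the spurious correlation. It assumed progression at 3 months plus an exponential time with median 3 months, tissue 1.5 months later and independent later survival with median 6 months. PD-L1 drifted by 0, 0.25, 0.5 or 1.0 SD per SD of time to tissue.

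- Spearman correlation with PFS: 0.00, 0.20, 0.37, 0.60.
- With OS from the early origin: 0.00, 0.11, 0.20, 0.31.
- With survival from the tissue date: 0.00 throughout.

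**3. Shared specimen.** Section 10.1 assumes 15 operated subjects and 12 with true progression and surgery. By subtraction 15 − 12 = 3 specimens would be tumour-free; the plan does not state this number. Suppose PD-L1 is scored on tumour cells and these 3 are recorded as negative. Fisher's exact two-sided p is then:

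- 12 of 12 against 0 of 3 positive: 1/C(15,3) = 1/455 = 0.002.
- 9 of 12 against 0 of 3: C(6,3)/455 = 20/455 = 0.044.
- 8 of 12 against 0 of 3: C(7,3)/455 = 35/455 = 0.077.

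The first two would be reported as significant with no biology behind them; the third would not.

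**The case against.** Section 8.5.2 leaves outcomes undefined, and Section 10.2 contains no explicit test of PD-L1 against OS or against true versus pseudoprogression. For tissue it specifies only a before/after comparison. The Spearman and Fisher tests above are therefore readings of generic wording. That is fair, but 8.5.2 does commit to the correlation, and the only outcome dates available are those in 8.2.1.

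The scoring point also has force. The documents give no PD-L1 scoring rule, and Section 4.7 places PD-1 ligands on several cell types, including vascular endothelium. Tumour-free inflamed tissue is not shown to be unscorable, so the circularity is conditional. The Yes/No paired test in 10.2 is worded as PD-1 receptor expression, so a claim that tumour-free tissue would be counted there as loss of PD-L1 does not follow from the text. Inconclusive histology is also possible (Section 8.1).

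A reader might infer that every outcome either precedes this tissue or is defined by it. The documents do not support that. Death follows the tissue, and follow-up runs to death. Subjects whose biopsy suggests pseudoprogression stay on treatment, so later progression can follow it as well. Imaging such as rCBV near the time of surgery is not defined by histology, so its correlation with PD-L1 is not circular. The archival and pre-enrolment samples are unaffected.

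Finally, the analyses are exploratory and unpowered, and 10.2 allows them to be reduced to description. That lowers the stakes but does not make a misdated outcome informative.

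**Conclusion.** The point holds for the progression tissue only. That the first progression date precedes the tissue follows from the plan's own definitions and needs no assumption. The OS bias is conditional on PD-L1 drifting with time on treatment. For n = 15, equal mean times before and after surgery and assumed correlations of 0.3, 0.5 and 0.7, false significance is about 8–10%, 16–22% and 25–42%; the lower figures include a diagnosis-to-treatment gap. It is lower at n = 10 and about 5% without drift. The circularity in true versus pseudoprogression is conditional on tumour-cell scoring. The primary endpoint, treatment and safety are not affected. The impact is minor, but a better analysis is available at almost no cost.

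**What to change.** In Sections 8.5.2 and 10.2:

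1. Correlate best response, PFS and OS from diagnosis only with pre-treatment PD-L1.
2. Relate progression-tissue PD-L1 only to events after it, counting survival and any later progression from the surgery date. Keep the cross-sectional correlation with contemporaneous imaging such as rCBV.
3. State the PD-L1 scoring rule. If the assay scores tumour cells, report tumour-free specimens as not assessable rather than negative, and do not test tumour-cell PD-L1 against histology-defined true versus pseudoprogression.

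This takes a few sentences of SAP text and no new data, since surgery dates and histology arise from the planned procedures. The price is a few exploratory PD-L1 values (about 3 on the plan's figures) and one exploratory contrast, both only under tumour-cell scoring.
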